6.1.4. Handling of Dropouts or Missing Data

6.1.4.1. Imputation of Missing Data

6.1.4.1.1. Imputation for the primary estimand

Any subject who prematurely withdraws from the study will have their last available data assigned to an analysis window as described in [Section 6.1.5](#). For subjects who discontinue due to lack of efficacy or adverse event, the last dose day will be assigned to an analysis window similarly as described in [Section 6.1.5](#). To comply with the definition of the primary estimand (Section 8.1.1), efficacy data assigned to a pre-specified analysis visit will be removed from the source data used for the multiple imputation process for visits on or after the assigned analysis visit of the last dose day for these subjects. Similarly, SI-NRS and WI-NRS weekly averages will be removed from the source data used for multiple imputation for weeks on or after the assigned analysis week of the last dose day for these subjects. This procedure will ensure that the data collected after intercurrent events are not used in the imputation process.

For the co-primary and secondary efficacy endpoints (i.e., S-IGA, B-IGA, weekly average SI-NRS, weekly average WI-NRS, total PSD score = 0, aggregated PSD score of itching, pain and scaling, PSD score of scaling item of 0, PSD score of the itching item of 0, PSD score of pain item=0, PASI, and PSSI), the analysis will impute missing values using a regression-based multiple imputation model. This is a three-step process.

1. The first step is to understand the pattern of missingness. In order to perform the multiple imputation, a monotone missing pattern has to be achieved. For example, if there exist values for baseline and Week 8 visits, but missing values for the Week 2 or 4 visits, Markov-Chain Monte-Carlo (MCMC) method will be used to impute the small amount of missing data that may be missing at the intermediate visits that is required to make the missing data pattern monotone before applying the multiple imputation algorithm. This method uses a non-informative Jeffreys prior to derive the posterior mode from the expectation-maximization (EM) algorithm as the starting values for the MCMC method. MCMC method will use seed of 66447809. All the endpoints will be considered as continuous for this step. To avoid values that could not be observed in practice for S-IGA, B-IGA, total PSD score, and PSSI, imputed values will be constrained to be integers in the range of the observed endpoint. Since SI-NRS and WI-NRS scores will be calculated as average weekly scores and PASI is a derived score that can have non-integer results (see [Section 6.1.7](#) for more information), this restriction will not apply for those endpoints. Total of 10 imputations are done in the MCMC step.
2. Once the monotone pattern is achieved, the next step is to implement the imputation algorithm. For this, the Predictive Mean Matching method (PMM) will be used. This method is particularly helpful if the normality assumption is violated. For subjects with complete data up to a particular visit, a PMM model will be fit that includes the outcome at that visit as the dependent variable and as independent variables, the outcome at previous visits, pooled site, and treatment group using a seed of 90066927. This process will be repeated 15 times, resulting in a total of 150 complete analysis datasets. The seed may be changed after unblinding in case of any issues with the imputation process, and it will be documented in the CSR if any change is required.
3. For each completed dataset, compute the necessary derived variables. The categorical endpoints will be analyzed using the CMH analysis for each of the complete analysis data sets stratified by pooled site group, baseline S-IGA category, and baseline B-IGA category. The results will be combined into one multiple imputation inference (odds ratio, associated CI, and *P* value) using PROC MIANALYZE as illustrated⁴. The continuous endpoints will be analyzed using descriptive summaries, and an ANCOVA for each of the complete analyses data sets with terms for the baseline outcome, pooled site group, baseline S-IGA category, and baseline B-IGA category as covariates. The descriptive summaries will use the averaged imputed outcomes across all datasets for each subject, and the ANCOVA results will be combined into one multiple imputation inference (LS means, standard errors [SEs], 95% CIs, 97.5% CIs, and *P* values) using PROC MIANALYZE as illustrated⁴.

This approach to imputation should be superior to other strategies such as carrying forward the last available observation, which may yield unrealistic imputed values. Also, the use of multiple

imputation avoids the problem of artificially increasing power through data imputation associated with single-imputation methods because it accounts for the uncertainty associated with the imputation. Other missing data will not be imputed, with the exception of incomplete dates as described in [Section 6.1.8](#). For responder analyses, missing data will be treated as a nonresponse with the exception of S-IGA and B-IGA. Only observed data will be summarized using descriptive statistics.

The SAS pseudo code for the multiple imputation process is listed below:

Step 1:

```
proc mi data=example seed=66447809 n impute=10 round=1 out=example_1;
  mcmc impute=monotone;
  var <baseline score> ..... <visit8 score>;
run;
```

Step 2:

```
proc mi data=example_1 seed=90066927 n impute=15 out=example_2;
  by <MCMC imputation>;
  class <treatment> <pooled site>;
  monotone regpmm(<baseline score> ..... <visit8 score>);
  var <treatment> <pooled site> <baseline score> ..... <visit8 score>;
run;
```

Step 3:

- For categorical outcomes, this step involves running a CMH test stratified by pooled site group, baseline S-IGA randomization strata, and baseline B-IGA randomization strata on each completed dataset and combining the results using PROC MIANALYZE.

```
proc freq data=example noprint;
  by <imputationnumber> <visit> ;
  tables <pooled site group> * <BL S-IGA randomization strata> * <BL B-IGA
randomization strata> * <treatment>
    * <outcome> / cmh commonriskdiff(cl=MH) alpha=0.025;
  output out=example_stat cmh;
run;
```

In order to apply PROC MIANALYZE for the categorical outcomes, normalizing transformations have to be applied to odds ratio. *P* values are obtained using Wilson Hilferty transformation as illustrated by Ratitch et.al.⁴

- For continuous outcomes, this step involves running an ANCOVA with terms for the baseline outcome, pooled site group, baseline S-IGA category, and baseline B-IGA category as covariates for each of the completed dataset and combining the results using PROC MIANALYZE

```
proc mixed data=example;
  by <imputationnumber> <visit> ;
  class <pooled site group> <BL S-IGA randomization strata> <BL B-IGA
randomization strata> <treatment>;
  model <outcome> = <pooled site group> <BL S-IGA randomization strata> <BL
B-IGA randomization strata>
    <treatment> <base> / alpha=0.025;
```

```
lsmeans <treatment> / alpha=0.025 pdiff cl;
ods output lsmeans=lsmeans
      diffss=diffss;
run;

*Combines the LS means across the MI datasets;
proc sort data=lsmeans;
  by <treatment> <imputationnumber>;
run;

proc mianalyze data=lsmeans;
  by <treatment>;
  modeleffects estimate;
  stderr stderr;
run;

*Combines the LS mean differences across the MI datasets;
proc sort data=diffss;
  by <treatment> <imputationnumber>;
run;

proc mianalyze data=diffss;
  by <treatment>;
  modeleffects estimate;
  stderr stderr;
run;
```

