6.1.4.2 Tipping Point Analysis

As a sensitivity analysis to the multiple imputation analysis as described in [Section 6.1.4.1](#) for the S-IGA and B-IGA co-primary endpoints, a tipping point analysis will be performed in order to determine the inflection point at which the inference under the MNAR assumption changes substantially. This will be used to check the robustness of the imputation.

The sensitivity analysis will be performed by using a specified sequence of shift parameters, which will adjust the imputed values for observations in both treatment groups. The range of shift parameters to be included in this analysis will be 0 to 2 by 0.5 for the active group and -2 to 0 by 0.5 for the vehicle group. Once the likely point of the shift is determined, the analysis may be rerun using a more focused range around the suspected tipping point. Thus, the value at which the results of the analysis are shifted from significant (i.e., $\alpha \leq 0.025$) to nonsignificant

(i.e., $\alpha > 0.025$) will be determined.

Step 1 and 3 of the analysis will be the same as for the multiple imputation analysis as described in [Section 6.1.4.1.1](#). However, [Step 2](#) of the analysis is where the shift parameters will be applied.

Pseudo-code for Step 2 is as follows:

```
proc mi data=example_1 seed=90066927 n impute=15 out=example_2;
  by <MCMC imputation>;
  class <treatment> <pooled site group.>;
  monotone regpmm(<baseline score> ..... <visit8 score>);
  var <treatment> <pooled site group> <baseline score> ..... <visit8 score>;
  mnar adjust(<visit2 score> / shift=YY adjustobs=(treatment='Roflumilast
Foam 0.3%));
  mnar adjust(<visit4 score> / shift=YY adjustobs=(treatment='Roflumilast
Foam 0.3%));
  mnar adjust(<visit8 score> / shift=YY adjustobs=(treatment='Roflumilast
Foam 0.3%));
  mnar adjust(<visit2 score> / shift=ZZ adjustobs=(treatment='Vehicle
Foam'));
  mnar adjust(<visit4 score> / shift=ZZ adjustobs=(treatment='Vehicle
Foam'));
  mnar adjust(<visit8 score> / shift=ZZ adjustobs=(treatment='Vehicle
Foam'));
run;
```

YY and ZZ will encompass all combinations of the range of shift parameters as pre-specified above.

Imputed values for subjects who discontinue due to lack of efficacy or adverse event will be handled as described in [Section 6.1.7](#) to ensure that these subjects are analyzed as non-responders at all visits on or after discontinuation of treatment.

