6.1.5. Analysis Visit Windows

6.1.5.1. Non-Diary Assessments

Visits will be analyzed as scheduled (i.e., not subject to visit windowing). Unscheduled, early termination, and/or repeated measurements will only be included if a scheduled measurement is not available and the unscheduled, early termination, or repeated measurement falls within the analysis visit windows as described in [Table 2](#). Visits falling outside of these windows will not be windowed (e.g., an unscheduled visit before first application of study drug). The windows follow the Schedule of Events in [Table 1](#). Unscheduled/repeated measurements will be listed.

Table 2: Analysis Visit Windows (Study Visit) for Non-diary Assessments

| Visit Name | Visit Number | Target Start Day | Lower Limit | Upper Limit |
|------------|--------------|------------------|-------------|-------------|
| Week 2 | 3 | 15 | 2 | 22 |
| Week 4 | 4 | 29 | 23 | 42 |

| Visit Name | Visit Number | Target Start Day | Lower Limit | Upper Limit |
|------------|--------------|------------------|-------------|-------------|
| Week 8 | 5 | 57 | 43 | --- |

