6.1.7. Derived Variables

Efficacy variable derivations described in this section will be performed with one exception. The exception is that subjects who discontinued early from study due to an AE or lack of efficacy will be considered as not having response (for MI and non-responder imputation analyses) and will be excluded from observed case analyses for all pre-specified analysis visits (refer to Section

6.1.5) on or after the associated analysis visit of the subject's last dose day). More specifically, for MI and non-responder imputation analyses, these subjects will be counted as non-responders for categorical variables and set to baseline for continuous variables for all visits on or after the associated analysis visit of the subject's last dose day.

- **Study day** is calculated as:
 - observation date – first dose date + 1, if record is collected on or after first dose date
 - observation date – first dose date, if record is collected prior to first dose date.
- **S-IGA Success** = S-IGA of “Clear” or “Almost Clear” plus at least 2-grade improvement from baseline.
- **B-IGA Success** = B-IGA of “Clear” or “Almost Clear” plus at least 2-grade improvement from baseline.
- **Average Weekly SI-NRS Score** = SI-NRS scores will be assigned to a particular study week based on the study week window, as shown in [Section 6.1.5.2](#). Average weekly baseline SI-NRS is derived as the average of all non-missing scores reported during the last 7 days prior to treatment if at least 4 of 7 evaluable daily SI-NRS questionnaires are available. Daily baseline SI-NRS is defined as the last non-missing assessment prior to the first study treatment.

If 2 or more observations are present for a single day, the most severe itch score will be used as a single daily value before calculating the average weekly score. The average of the reported (non-missing) SI-NRS scores assigned to each study week will be calculated. If at least 4 SI-NRS scores are present in this time period, the average weekly SI-NRS score will be calculated; otherwise, the average weekly score will be missing for that week. The derived average score will be rounded to 1 digit. Missing average weekly scores will be imputed as described in [Section 6.1.4.1](#).

- **SI-NRS Success** = achievement of at least 4-point reduction in average weekly SI-NRS score compared to baseline, calculated only for the subjects with SI-NRS ≥ 4 at baseline.

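### The composite rule runs from the analysis window of the last dose rather than its date, so on-treatment Week 2 and Week 4 results become failures and a Day 1 last dose has no starting visit

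*SAP*

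**What the plan says.** SAP 6.1.4.1.1, 6.1.7 and 8.1 give one rule for subjects who discontinue because of an adverse event or lack of efficacy. First, "the last dose day will be assigned to an analysis window similarly as described in" Section 6.1.5. Efficacy data are then removed "for visits on or after the assigned analysis visit of the last dose day for these subjects", and weekly itch averages are treated the same way by analysis week. In the multiple-imputation and non-responder analyses, "these subjects will be counted as non-responders for categorical variables and set to baseline for continuous variables" from that visit on.

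The purpose is stated in the same section: "This procedure will ensure that the data collected after intercurrent events are not used in the imputation process". SAP 6.1.4.2 describes the intended result as these subjects being "analyzed as non-responders at all visits on or after discontinuation of treatment".

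The windows are in SAP 6.1.5.1, Table 2: Week 2 is Days 2-22, Week 4 is Days 23-42 ("Week 4 | 4 | 29 | 23 | 42"), and Week 8 is Day 43 onward. There is no Baseline or Day 1 row. For clinic data the section says "Visits will be analyzed as scheduled (i.e., not subject to visit windowing") and "Visits falling outside of these windows will not be windowed". Under SAP 6.1.7 the first dose date is study Day 1.

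**The concern.** The windows in Table 2 were built to place stray visits. Here they decide from when a subject counts as a failure, and they are wide compared with the visit tolerances (±3 days at Week 2, ±5 days at Week 4). Two mismatches follow.

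(a) A clinic result obtained on treatment, before the subject stopped, is overwritten if the last dose falls later in the same window. Take a subject seen on Day 29. With a last dose on Day 42 the Week 4 result becomes a failure; with a last dose on Day 43 the same result is kept. Nothing known on Day 29 differs. Under SAP 6.1.3 the exposed alpha-controlled endpoints are S-IGA Success at Weeks 2 and 4, PASI change at Week 2, and the endpoints built on weekly itch averages.

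(b) A subject whose only dose was on Day 1 is among the clearest cases for the composite strategy, yet Day 1 is in no Table 2 window. SAP 6.1.4.1.1 treats missing data as non-response in responder analyses but exempts S-IGA and B-IGA. Read literally, such a subject is multiply imputed and can be a responder on both co-primaries. An early termination visit on Days 2-22 would also be windowed to Week 2 and enter the imputation as post-event data.

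**Working it through.** **Plan's own figure.** SAP 3.2 states more than 99% power for each co-primary, with 280 v 140 subjects and 2-sided α = 0.025. The rates are read as active v vehicle 46% v 11% (S-IGA) and 32% v 7% (B-IGA); the text prints the arms in reverse. Unstratified normal approximation:

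power = Φ{[Δ − 2.2414·√(p̄(1−p̄)(1/280 + 1/140))] / √(pA(1−pA)/280 + pV(1−pV)/140)}

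- S-IGA: p̄ = (280×0.46 + 140×0.11)/420 = 0.343; Φ[(0.35 − 0.1102)/0.03983] = Φ(6.02), above 99.99%.
- B-IGA: p̄ = (280×0.32 + 140×0.07)/420 = 0.237; Φ[(0.25 − 0.0986)/0.03524] = Φ(4.30), 99.999%.

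Both reproduce. The point does not depend on them; they only bound how much it can matter for the co-primaries.

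**(a) Clinic visits.** For a visit on day v in a window ending on day U, a last dose on any of days v+1 to U overwrites that visit, which is U − v days.

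| Window | Length | Visit on target | Range over visit tolerance |
|---|---|---|---|
| Week 2, Days 2-22 | 21 | Day 15: 22 − 15 = 7 (33%) | Day 12: 10; Day 18: 4 |
| Week 4, Days 23-42 | 20 | Day 29: 42 − 29 = 13 (65%) | Day 24: 18; Day 34: 8 |

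Protocol 5.2.1.1 and 5.2.1.2 put the IGAs before application, so a last dose on the visit day also follows the assessment. Counting it gives 8 of 21 (38%) and 14 of 20 (70%). These are shares of window days, not of subjects.

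**(a) Weekly itch (Table 3).** A last dose on Day 14 voids Week 2 (Days 8-14), although all seven days were on treatment. With a complete diary, last doses on Days 11-14 leave at least the 4 scores that SAP 6.1.7 requires, yet the week is still voided. The same holds for 4 of 7 days in each of Weeks 2-8, and for Days 5-7 in Week 1.

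**(a) Week 8 clinic endpoints.** Every last dose from Day 2 on maps to Week 2, 4 or 8, so Week 8 is always non-response for these subjects. The Week 8 visit normally follows the last dose, so no pre-event result is lost there. For visits inside the protocol tolerances and a last dose on Day 2 or later, no post-event visit escapes the rule either.

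**(b) Day 1 last dose.** Let f be the share of the active arm whose only dose was on Day 1. The documents give no value; 0.5% to 3% is assumed (1.4 to 8.4 of 280). If these subjects are imputed near the arm rate p, the arm shows p; under the composite rule it shows p(1 − f). The overstatement is p·f:

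- S-IGA: 0.46×0.005 = 0.23 points, to 0.46×0.03 = 1.38 points.
- B-IGA: 0.32×0.005 = 0.16 points, to 0.32×0.03 = 0.96 points.

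With f = 3% scored as failures, power stays above 99.99% for both.

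**After the fix.** On-treatment clinic visits overwritten: 0 of 21 and 0 of 20 last-dose days. Day 1 stoppers are non-responders at Weeks 2, 4 and 8.

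**The case against.** The window rule is stated consistently in several places. Under a composite strategy the event is part of the outcome, so failing the whole interval that contains it is a coherent choice. The regulatory advice quoted in SAP 1 calls such subjects non-responders without a date cut, and removing a whole window does keep post-event data out. All of that is fair. But the rule is not a whole-subject failure rule, since earlier windows stay observed, and it removes more than the stated purpose requires.

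On Day 1, SAP 6.1.4.1.1 says only that the last dose day is assigned similarly to 6.1.5. A programmer could treat Day 1 as the scheduled Baseline visit and fail everything after it. Table 3 has a Baseline row that can include Day 1, and SAP 8.1 plainly intends these subjects to be non-responders. This stands: (b) is a gap in wording, not a decision to exempt anyone. A reader might infer that Day 1 stoppers are deliberately left out of the composite rule; the documents do not support that.

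Other planned analyses give partial cover. The treatment-policy estimand (6.1.4.1.2) restores the overwritten visits, but it also restores post-event data, so it does not isolate the effect. Non-responder imputation (8.1.4, 8.2) fails a Day 1 stopper who has no later data, but SAP 6.1.7 applies the same window rule there, so it does not undo (a).

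**Conclusion.** The mismatch is real and worth correcting, but limited. Part (a) follows directly from the text. It reaches S-IGA Success at Weeks 2 and 4, PASI change at Week 2 and the weekly itch endpoints. Its extent depends on visit timing: 4-10 of 21 and 8-18 of 20 last-dose days across the tolerances. A reader might infer that it alters the Week 8 co-primaries or inflates response; it does neither. Week 8 clinic endpoints are untouched, and for responder endpoints (a) can only turn successes into failures. Its effect on the treatment difference depends on how stops divide between the arms, which the documents do not give.

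Part (b) does concern the co-primaries, but only on a literal reading, and its size rests on an assumed 0.5-3% rate in the active arm and on imputation near the arm rate. Neither part threatens co-primary power. The number of subjects affected by either part is unknown.

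The strongest reason to settle the wording is timing. SAP V3.0 was written after database lock and unblinding, so any unstated mapping would be chosen with treatment codes open.

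**What to change.** For subjects who discontinue for an adverse event or lack of efficacy, state in SAP 6.1.4.1.1, 6.1.7 and 8.1:

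- **Attended visits:** non-response (or baseline value) at every scheduled visit whose actual assessment date is after the last dose date. Clinic assessments dated on or before the last dose date stay as observed.
- **Unattended visits:** non-response (or baseline value) at every visit whose target day is after the last dose day. Without this, a visit that never took place has no date and would escape a pure date comparison.
- **Day 1:** a Day 1 last dose means non-response at all post-baseline visits.
- **Diary:** compute the weekly average from days up to the last dose if at least 4 scores exist. Otherwise apply the composite rule to that week. Apply it to all later weeks in either case.

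The programming cost is small: a date comparison and a rerun of the affected tables. The greater cost is that this is a further post-unblinding change to the derivation for the primary estimand. Document it as such, list the affected subjects by arm, and report results under both the window rule and the date rule.

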3.3. Study Population

Study population consists of male and female adolescents (12-17 years old) and adults (≥ 18 years old). Subjects should have a minimum S-IGA of at least “Moderate” (3) and B-IGA

of at least “Mild” (2) at baseline.

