6.1.2. Adjustments for Covariates

Covariates for this study include the pooled site group (see [Section 6.1.6](#)), baseline S-IGA randomization strata (S-IGA = 3 vs. S-IGA =4) and baseline B-IGA randomization strata (B-IGA = 2 vs. B-IGA \geq 3).

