8. EFFICACY ANALYSIS

Efficacy analysis will be based on ITT population unless specified otherwise. The randomized treatment arm and strata will be used in the efficacy analysis.

The efficacy analyses that include the stratification factors (pooled sites, baseline S-IGA and baseline B-IGA) will use the strata data as collected in the interactive web response system (IWRS). A table of randomized strata vs. actual strata will be provided if there are any differences.

The order of testing for the co-primary and secondary endpoints is discussed in [Section 6.1.3](#). Other secondary efficacy endpoints are not included in the testing strategy.

Data analyzed using CMH methodology will be based upon the following code:

```
proc freq data=example noprint;
  by <visit>;
  tables <pooled site group> * <BL S-IGA randomization strata > * <BL B-IGA
randomization strata > * <treatment>
  * <outcome> / cmh commonriskdiff(cl=MH) alpha=<0.025 or 0.05>;
  output out=example_stat cmh;
run;
```

If a non-estimable odds ratio and associated p-value occur as part of the multiple testing strategy, the p-value to be used in the testing strategy will be based on a test of a difference in proportions. In cases where the odds ratio and difference in proportion are non-estimable, the stratification factors will be removed. Statistical significance will be concluded at the 2.5% significance level (2-sided) or less, as discussed in Section 6.1.3. Odds ratios, 95% CIs, and 97.5% CIs for the odds ratios and differences in percent will be provided, whenever possible.

Data analyzed using ANCOVA will be based upon the following code:

```
proc mixed data=example;
  by <visit>;
  class <treatment> <pooled site group> <BL S-IGA randomization strata > <BL
B-IGA randomization strata >;
  model <outcome> = <treatment> <pooled site group> <BL S-IGA randomization
strata > <BL B-IGA randomization strata > <baseline value> / alpha=<0.025 or
0.05>;
  lsmeans trtn / alpha=<0.025 or 0.05> pdiff cl;
run;
quit;
```

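### The Step 2 imputation model omits randomisation strata used in the main analyses: the other region's stratum for S-IGA and B-IGA, and both strata for the itch, PASI, PSSI and PSD endpoints.

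*SAP*

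**What the plan says.** SAP Section 6.1.4.1.1 describes the Step 2 regression as having, "as independent variables, the outcome at previous visits, pooled site, and treatment group". The code agrees: "var <treatment> <pooled site> <baseline score> ..... <visit8 score>". The tipping-point version in Section 6.1.4.2 carries the same list: "var <treatment> <pooled site group> <baseline score> ..... <visit8 score>". None of the three names the S-IGA or B-IGA stratum.

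The analysis side is richer. Section 6.1.2 begins "Covariates for this study include the pooled site group" and goes on to list both IGA randomisation strata. In Step 3, binary endpoints are analysed by CMH, "stratified by pooled site group, baseline S-IGA category, and baseline B-IGA category", and continuous endpoints by ANCOVA with "terms for the baseline outcome, pooled site group, baseline S-IGA category, and baseline B-IGA category as covariates". Section 8 adds that analyses using the stratification factors "will use the strata data as collected in the interactive web response system (IWRS"). The SAP gives no reason for leaving the two strata out of Step 2.

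**The concern.** An imputation model should contain at least the covariates of the analysis that it feeds. If it does not, missing at random has to hold given fewer variables than the trial holds, and imputed values show a weaker stratum effect than observed values do. Both strata are randomisation factors, so they are known for every randomised subject and cannot themselves be missing.

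Multiple imputation is the primary method in Table 5 for all co-primary and secondary endpoints. The endpoints that lack both strata include all seven in Family 2, tested in sequence at 0.005, and the SI-NRS endpoints of Family 1. One failure in Family 2 stops its alpha from passing to Family 1, so a small avoidable loss could in principle carry forward. The sensitivity analyses in Section 8.1.4 do not isolate the omission. The tipping-point analysis inherits the same predictor list, and the observed-case and non-responder analyses replace the missing-data assumption altogether.

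**Working it through.** **1. The plan's own figures.** The number of completed data sets is 10 × 15 = 150, as stated. Power was checked with 280 and 140 subjects, two-sided alpha 0.025 and an unstratified normal approximation:

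power = Φ{[Δ − 2.2414·√(p̄q̄(1/280 + 1/140))] / √(p₁q₁/280 + p₀q₀/140)}

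- S-IGA, 11% vs 46%: (0.35 − 0.1102)/0.0398 = 6.02, so power is above 99.99%.
- B-IGA, 7% vs 32%: (0.25 − 0.0986)/0.0352 = 4.30, so power is about 99.999%.

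Both agree with the stated figure of more than 99%. The lower rate is taken as vehicle; the arm labels in SAP Section 3.2 appear to be swapped. Adding predictors to Step 2 changes none of these figures.

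**2. Predictors against analysis factors.** The Step 2 variable list includes the baseline score of the endpoint being imputed. SAP Section 3.3 says "Subjects should have a minimum S-IGA of at least “Moderate” (3) and B-IGA" of at least 2. On a 0–4 scale, baseline S-IGA is therefore 3 or 4, the same split as its stratum. Baseline B-IGA is 2, 3 or 4, which is finer than its stratum.

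| Endpoint imputed | Pooled site | S-IGA stratum | B-IGA stratum | Analysis factors missing |
|---|---|---|---|---|
| S-IGA | in model | carried by baseline score | absent | 1 of 3 |
| B-IGA | in model | absent | carried by baseline score | 1 of 3 |
| SI-NRS, WI-NRS, PASI, PSSI, PSD | in model | absent | absent | 2 of 3 |

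The baseline score is a near-exact substitute for its own stratum, not a guaranteed one, because the analysis uses IWRS strata and these can differ from the recorded score.

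**3. Size for S-IGA when the B-IGA stratum is left out.** The documents give no planning rate for missing data and no stratum effect, so these are assumptions. The simulation used 420 subjects randomised 2:1, 20 pooled sites, 20% with S-IGA 4, 60% with B-IGA ≥3, one post-baseline visit, 5 donors, 10 imputations and 60 replicates. The log odds of being missing were 0.5 higher with B-IGA ≥3. Entries are mean Mantel-Haenszel log odds ratios, stratified on all three factors.

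| Missing | Stratum effect | Complete data | Without stratum (SE) | With stratum (SE) | Without − complete |
|---|---|---|---|---|---|
| 5% | 0.3 SD | 1.959 | 1.969 (0.345) | 1.951 (0.347) | +0.010 |
| 5% | 0.8 SD | 1.994 | 1.963 (0.357) | 1.985 (0.358) | −0.031 |
| 10% | 0.3 SD | 2.035 | 2.009 (0.365) | 2.020 (0.366) | −0.026 |
| 10% | 0.8 SD | 2.027 | 1.969 (0.372) | 2.012 (0.378) | −0.058 |
| 20% | 0.3 SD | 1.987 | 1.976 (0.385) | 1.989 (0.395) | −0.011 |
| 20% | 0.8 SD | 1.999 | 1.929 (0.386) | 1.996 (0.405) | −0.070 |

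The largest gap is 0.070, or 0.070/0.386 = 0.18 standard errors, towards the null. With 60 replicates the Monte Carlo error of a single mean is about 0.39/√60 = 0.05. Columns within a row share the same simulated trials, so their differences are more precise than that, but gaps of 0.01 to 0.03 should not be interpreted.

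**4. Size for an endpoint that lacks both strata.** A PSSI-75-type endpoint was simulated with 420 subjects, 28 pooled sites, 300 trials and 6 imputations. It assumed 9–12% missing at Week 8, 15% with S-IGA 4, and S-IGA 4 lowering improvement by 10–20 percentage points of baseline. Leaving the strata out overstated success by 3–6 points among S-IGA 4 subjects with missing data; with them in, the error was −0.5 to −0.9 points. In the strongest case the active-arm bias fell from 0.40 to 0.12 points, a change of 0.28 points, or 0.0028 × 280 = 0.8 of a subject. In the mildest cases it barely changed.

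**The case against.** Predictive mean matching already conditions on the subject's own baseline and earlier scores, and PSSI and PASI measure the same signs that the IGA strata summarise. Only the stratum information left after those scores is lost. A reader might infer that severe subjects who drop out are imputed as if they were average; for that reason the documents do not support it. Nor does Step 2 decide the result for everyone. Under the primary estimand, Section 6.1.7 sets subjects who discontinue for an adverse event or lack of efficacy to non-response, or to baseline for continuous endpoints, whatever was imputed. That removes a plausible route from severity to biased imputation. Neither simulation establishes a material effect, and planned power exceeds 99%. Finally, changing the primary imputation model after unblinding has a cost of its own, and the agency advice quoted in the SAP Overview does not ask for it.

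Most of this stands, and it limits the size of the point and the form of the remedy. It does not remove the omission, for which the SAP gives no reason. The override also does not apply under the supplemental estimand (Section 6.1.4.1.2), where these subjects are treated like all others.

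**Conclusion.** The omission is plain in the Step 2 text, the Step 2 code and the tipping-point code. Its expected effect is small: at most 0.070 on the S-IGA log odds ratio scale, and 0.28 percentage points in the active arm for a PSSI-75-type endpoint, in the strongest cases tried. These sizes rest on assumed missing rates, stratum frequencies and stratum effects. The S-IGA simulation had no intermediate visits and did not apply the non-response override, so it gives an order of magnitude only.

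Three stronger readings are not supported:

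- That co-primary imputations ignore two of the three analysis factors. Each ignores one, because the endpoint's own baseline score is in the model.
- That every analysis model uses both strata. The severity subgroup models drop the matching stratum (Section 8.4), and stratification is dropped when neither the odds ratio nor the difference in proportions can be estimated (Section 8).
- That a co-primary conclusion is in doubt. Nothing here shows that.

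It is a specification gap worth closing because closing it costs little.

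**What to change.** In Step 2 of Section 6.1.4.1.1 and in its copy in Section 6.1.4.2, add to the `CLASS` statement, and to the `VAR` list ahead of the scores:

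- the IWRS B-IGA stratum when S-IGA is imputed;
- the IWRS S-IGA stratum when B-IGA is imputed;
- both IWRS strata when SI-NRS, WI-NRS, PASI, PSSI or PSD is imputed.

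Placing them ahead of the scores makes them predictors for every visit. The endpoint's own stratum should not be added for S-IGA or B-IGA, since it would nearly duplicate the baseline score. Amend the Step 2 sentence on predictors to match.

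Because SAP Version 3.0 was written after database lock and unblinding, leave the specified model as the primary one. Report the corrected model beside it as a clearly labelled sensitivity analysis for the co-primary and multiplicity-controlled secondary endpoints. The cost is one or two binary terms in each imputation model, one changed sentence and a little extra analysis work. No new data are needed, and sample size, alpha and the 150 data sets are unaffected.
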